Section 13.1 Sample Size, Power and Significance Levels p. 112	
(...) A total of 192 patients will be enrolled. The 192 patients will be randomly allocated on a 1:1:1 basis (25 mg/kg/day GWP42003-P, 50 mg/kg/day and placebo, 64 patients per group). Patients in the placebo group will be split into two cohorts (32 patients 25 mg/kg/day dosing volumes and 32 patients receiving 50 mg/kg/day dosing volumes), but it is assumed that these two cohorts can be pooled for the analyses of efficacy. If it is assumed that patients in the placebo group will experience a mean reduction in seizure frequency of 15% (from baseline), this sample size of 64 patients per group will be sufficient to detect a difference of 35% between treatments (i.e., patients receiving GWP42003-P will experience at least a 50% reduction in seizures). This is based on a standard
	
(...) A total of 210 patients will be enrolled. The 210 patients will be randomly allocated on a 1:1:1 basis (25 mg/kg/day GWP42003-P, 50 mg/kg/day and placebo, 70 patients per group). Patients in the placebo group will be split into two cohorts (35 patients receiving 25 mg/kg/day dosing volumes and 35 patients receiving 50 mg/kg/day dosing volumes), but it is assumed that these two cohorts can be pooled for the analyses of efficacy. If it is assumed that patients in the placebo group will experience a mean reduction in seizure frequency of 15% (from baseline), patients receiving GWP42003-P will experience at least a 50% reduction in seizures and a common standard deviation of 60%, then this sample size of 70 patients per group will be sufficient
	
See Section 2.3 See Section 2.3

Revised Protocol Section Number, Heading and Page Number	Original Wording from Clinical Protocol Version 2 Date 21 OCT 2015 (Deleted wording is struck through and in bold)	Revised Wording from Clinical Protocol Amendment 2 (Clinical Protocol V3 25Aug16) (Revised wording is underscored and in bold)	Rationale for the amendment
Section 13.1 Sample Size, Power and Significance Levels p. 112 (Continued)	deviation of 60%, using a two-sided 5% significance level and 90% power.	to detect a difference in response distributions with 90% power. This test is based on a two-sided non-parametric Wilcoxon-Mann-Whitney test for continuous response data with a 5% significance level.	

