Section 13.6.2 Primary Endpoints p. 115	
(...) If the data are found to be normally distributed, they will be analyzed using an analysis of covariance (ANCOVA) approach. The model will include baseline and age group as covariates and treatment group as fixed factor. The treatment difference, together with the 95% confidence intervals (CIs) will be presented. A step down procedure will be used to control the type I error as per Section 13.6. However, due to the nature of seizure data, if a normal distribution cannot be assumed, the data will be analyzed using a Wilcoxon rank-sum test. An
	
(...) Data will be analyzed using a Wilcoxon rank-sum test. An estimate of the median difference between each GWP42003-P group and placebo, together with approximate 95% CI, will be calculated using the Hodges-Lehmann approach. A step-up Hochberg's procedure will be used to control the Type I error as per Section 13.6.
	See Section 2.3

Revised Protocol Section Number, Heading and Page Number	Original Wording from Clinical Protocol Version 2 Date 21 OCT 2015 (Deleted wording is struck through and in bold)	Revised Wording from Clinical Protocol Amendment 2 (Clinical Protocol V3 25Aug16) (Revised wording is underscored and in bold)	Rationale for the amendment
Section 13.6.2 Primary Endpoints p. 115 (Continued)	
estimate of the median difference between 50 mg/kg/day GWP42003 P and placebo, together with approximate 95% CI, will be calculated using the Hodges-Lehmann approach. The comparison of 25 mg/kg/day GWP42003 P and placebo will be presented, but the Wilcoxon rank-sum test only performed if the comparison of 50 mg/kg/day GWP42003 P and placebo is statistically significant at the 5% level.
 
A graphical assessment of normality will be performed as well as computation of summary statistics for normality using the Shapiro-Wilk statistical test. If it is assumed that normality does hold, then a sensitivity analysis will be performed using the Wilcoxon rank-sum test as described above.
		See Section 2.3

Revised Protocol Section Number, Heading and Page Number	Original Wording from Clinical Protocol Version 2 Date 21 OCT 2015 (Deleted wording is struck through and in bold)	Revised Wording from Clinical Protocol Amendment 2 (Clinical Protocol V3 25Aug16) (Revised wording is underscored and in bold)	Rationale for the amendment

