Section 13.6.2.1 Sensitivity Analysis for the Primary Endpoint p. 116-118 (Continued)	
the treatment period:
 
 The model will include baseline and age group as covariates and treatment group as a fixed factor. The time variable will be the assessment time point (nominal visit number, corresponding to each 21 days of the double-blind period) treated as a categorical repeated factor. The baseline by-time and treatment by-time interactions will also be included. The model will have an unstructured covariance matrix. The fitted model will then be used to produce a final time point comparison, which implicitly adjusts for missing observations under the assumption of missing at random (MAR); there will be no imputations for missing values at individual time points. The time course of the treatment effect will also be examined by estimating treatment differences, together with their 95% CIs, for each nominal visit during the randomized treatment period. A step-down procedure will be used to control the 	
seizures (average per 28 days) during the treatment period.
 
 The ranks of the percentage change from baseline and the baseline number of seizures (average per 28 days) will be calculated. The rank of the percentage change from baseline will then be analyzed using an ANCOVA model with the rank of the baseline number of seizures (average per 28 days) and age group (1–6 years, 7–11 years, 12–17 years and 18–65 years) as covariates and treatment group as a fixed factor. The estimated least squares means, treatment differences, together with the 95% CIs and p-value will be presented. ANCOVA of log transformed number of seizures (average per 28 days) during the treatment period. The number of seizures (average per 28 days) during the treatment period and the baseline number of seizures (average per 28 days) will be log transformed prior to analysis. The log 	See Section 2.3

Revised Protocol Section Number, Heading and Page Number	Original Wording from Clinical Protocol Version 2 Date 21 OCT 2015 (Deleted wording is struck through and in bold)	Revised Wording from Clinical Protocol Amendment 2 (Clinical Protocol V3 25Aug16) (Revised wording is underscored and in bold)	Rationale for the amendment

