
Section 13.6.3 Secondary Endpoints p. 118-120 (Continued)
	
seizure-free days, number of seizures by subtype, number of infantile/epileptic spasms, use of rescue medication, number of episodes of status epilepticus, Vineland-II, Wechsler scales, CBCL, ABCL, SCQ, QOLCE, QOLIE-31-P, SGIC/CGIC and PGIC scores, the data will be summarized at baseline and over the treatment period, and at each time point (or 28-day period, as appropriate) during the maintenance period. Changes from baseline to the average over the treatment period (or at end of study) will be analyzed using ANCOVA, as with the primary endpoint (or appropriate non-parametric methods if data are found to be not normally distributed). SGIC-SD/CGIC-SD assessments recorded at the end of treatment will be analyzed with ordinal logistic regression using the proportional odds model. Changes from baseline for IGF-1 levels will be summarized by treatment group and plotted against the Tanner Stages, weight, and height. Tanner Stages will be evaluated and summarized descriptively at each time point in terms of frequency
	
Cochran–Mantel–Haenszel test stratified by age group. In addition, the difference in proportions and the odds ratio, together with 95% CIs, comparing the treatment groups will be presented.
 
For changes in composite focal seizure score, number of seizure-free days, use of rescue medication, number of episodes of status epilepticus (only if there is a sufficient number of patients with data), Vineland-II, Wechsler scales, CBCL, ABCL, SCQ, QOLCE and QOLIE-31-P scores, the data will be summarized at baseline and over the treatment period, and at each time point (or 28 day period, as appropriate) during the maintenance period. Changes from baseline to the average over the treatment period (or at end of study) will be analyzed using ANCOVA (or appropriate non-parametric methods if data are found to be not normally distributed). The models will include baseline and age group as covariates and treatment group as fixed factor. The treatment difference, together with the 95% confidence intervals (CIs) will be presented. The percentage change in total seizures, the number
	
See Section 2.3

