Revised Protocol Section Number, Heading and Page Number	Original Wording from Clinical Protocol Version 1, Date 16 Jun 15 (Deleted wording is struck through and in bold)	Revised Wording from Clinical Protocol Amendment 1 (Clinical Protocol Version 2, Date 21 Oct 15) (Revised wording is underscored and in bold)	Rationale for the amendment
Section 7.1 Treatment Assignment p. 56	(...) After confirmation of eligibility at Visit 2 , patients will be randomly allocated to 25 mg/kg/day, 50 mg/kg/day or placebo using the IVRS. (...)	(...) After confirmation of eligibility at Visit 3 , patients will be randomly allocated to 25 mg/kg/day, 50 mg/kg/day or placebo using the IVRS. (...)	See Section 2.3
Section 7.2 Randomization p. 56	(...) The randomization will be stratified by age group (2-6 years, 7-11 years, 12-17 years and 18-65 years).	(...) The randomization will be stratified by age group (1-6 years, 7-11 years, 12-17 years and 18-65 years).	See Section 2.5
Section 8.1 Investigational Medicinal Product Dosage, Administration and Schedule p. 57	(...) Patients will be assigned one of two Dose Levels of active IMP or placebo on a 1:1:1 basis (48 patients per treatment group). Patients in the placebo group will be split into two cohorts (24 receiving Low Dose Level dosing volumes and 24 receiving High Dose Level dosing volumes), but it is assumed that these two cohorts can be pooled for the analyses of efficacy.	(...) Patients will be assigned one of two Dose Levels of active IMP or placebo on a 1:1:1 basis (64 patients per treatment group). Patients in the placebo group will be split into two cohorts (32 receiving Low Dose Level dosing volumes and 32 receiving High Dose Level dosing volumes), but it is assumed that these two cohorts can be pooled for the analyses of efficacy.	See Section 2.6
Section 8.1.1 Dose Administration	The IMP will be administered orally by the patient or their caregiver twice each day (morning and evening) using the syringe(s) provided. The IMP will be	The IMP will be administered by the patient or their caregiver twice each day (morning and evening) using the syringe(s) provided and may be taken with other	See Section 2.8

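### The primary Wilcoxon test uses neither the age strata of the randomisation nor baseline seizure count; planned power is met, but a rank ANCOVA already written could add up to about 5 points

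*Protocol*

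**What the plan says.** The revised wording of Section 13.6.2 in Amendment 2 (protocol V3) reads "Data will be analyzed using a Wilcoxon rank-sum test. An estimate of the median difference between each GWP42003-P group and placebo", with an approximate 95% interval by the Hodges-Lehmann approach and Hochberg's procedure across the two doses. No stratum or covariate is named.

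Elsewhere age and baseline are used:

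- Section 7.2 (Amendment 1 wording): "The randomization will be stratified by age group", the groups being 1–6, 7–11, 12–17 and 18–65 years.
- Section 13.6.2.1, sensitivity analyses: the rank of the percentage change "will then be analyzed using an ANCOVA model with the rank of the baseline number of seizures" and four-level age group as covariates, and treatment as a fixed factor. An ANCOVA of log-transformed counts with baseline and age is listed as well.
- Section 13.6.3: the responder analyses, including the key secondary endpoint, use a Cochran–Mantel–Haenszel "test stratified by age group". The ANCOVA secondaries carry baseline and age group.

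Section 13.1 sizes the trial at 70 per group "to detect a difference in response distributions with 90% power", and adds: "This test is based on a two-sided non-parametric Wilcoxon-Mann-Whitney test for continuous response data with a 5% significance level".

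**The concern.** The analysis that decides the trial leaves out the factor that governed the randomisation, while the key secondary and the sensitivity models include it. Amendment 2 moved the primary analysis from ANCOVA to ranks. Its rationale (Section 2.3) covers the change of test and the larger sample, but gives no reason for leaving out age and baseline. Section 13.6.2.1 shows that ranks and adjustment can go together.

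Two things follow. If age predicts percentage change, stratified allocation balances it across arms, yet the unstratified test still counts the between-age variation as noise and is therefore conservative. If baseline count predicts percentage change, for example through regression to the mean after a single 28-day baseline, the plain test leaves that variation in as well. In both cases the trial forgoes precision available from data it already holds on every patient.

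**Working it through.** **1. Reproducing the planned sample size.** Inputs from Section 13.1: placebo reduction 15%, active reduction 50% (difference 35 points), common SD 60, two-sided 5%, 90% power, 1:1 for each dose against placebo. Under a normal shift:

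- P(X<Y) = Φ(35 / (60√2)) = Φ(0.4125) = 0.660.
- Noether: total N = (1.960 + 1.282)² / (12 × 0.25 × 0.160²) = 136.8, or 69 per arm, against 70 stated.
- Power at 70 per arm: Φ(√(12 × 0.25 × 140) × 0.160 − 1.960) = 90.6%.

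The stated figure reproduces for the unadjusted test.

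**2. What adjustment could add, by formula.** Let R² be the share of outcome variance explained by baseline and age together. The documents do not give it, so a range is assumed. The effective n per arm is about 70 / (1 − R²).

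| Assumed R² | Power at 5% | Power at 2.5% | n per arm for 90% at 5% |
|---|---|---|---|
| 0 | 90.6% | 85.0% | 69 |
| 0.05 | 92.0% | 86.9% | 65 |
| 0.10 | 93.3% | 88.8% | 62 |
| 0.20 | 95.6% | 92.3% | 55 |
| 0.25 | 96.6% | 93.9% | 52 |

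The 2.5% column matters because a dose must reach p < 0.025 under Hochberg if the other dose misses 0.05.

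**3. Simulation.** 6,000 trials per setting, 70 per arm, age-stratified allocation, SD 60, difference 35 points. The plain Wilcoxon is compared with a rank ANCOVA on baseline rank, four age groups and treatment. Gains are taken from unrounded figures.

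| Correlation with outcome: baseline, age | R² | Wilcoxon | Rank ANCOVA | Gain (points) |
|---|---|---|---|---|
| 0, 0 | 0.00 | 91.3% | 91.5% | 0.2 |
| 0.2, 0.1 | 0.05 | 92.0% | 93.3% | 1.3 |
| 0.3, 0.2 | 0.13 | 91.4% | 94.2% | 2.8 |
| 0.3, 0.3 | 0.18 | 92.0% | 95.6% | 3.7 |
| 0.4, 0.3 | 0.25 | 91.9% | 96.7% | 4.8 |

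At R² = 0.25 the formula implies 6.0 points (96.6 − 90.6), more than the simulated 4.8. The main reason is that the simulated Wilcoxon comparator sits about a point above the formula's 90.6%. The conclusion uses the simulated gains.

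**4. Type I error.** With an age correlation of 0.3 and no baseline effect, the simulated error was 3.8% for the plain Wilcoxon and 4.8% for the rank ANCOVA. The approximation P(|Z| > 1.96 / √(1 − 0.09)) gives 4.0%, which agrees within simulation error. With baseline correlation 0.3 and no age effect, the Wilcoxon error was 5.1%. The conservatism therefore comes from age, not baseline.

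**5. Is an R² of 0.05 to 0.25 plausible?** Percentage change ranks identically to the log ratio of treatment to baseline frequency. With equal log variances and baseline-to-treatment correlation r, its squared correlation with log baseline is (1 − r)² / (2(1 − r)) = (1 − r)/2: 0.25 at r = 0.5 and 0.05 at r = 0.9. Both r and the equal variances are assumptions, and the entry rule of at least eight baseline seizures would shrink these values. This shows that the range is possible, not that it applies here.

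**The case against.** The strongest reply is that nothing planned is missing. The sample size was built for exactly this unadjusted test and reproduces. The test is valid, and where it errs it errs on the safe side. Baseline is not wholly ignored either: it is the denominator of the endpoint, so only its residual association with percentage change could be recovered. Adjusted analyses are already prespecified, so robustness to adjustment will be visible. The Wilcoxon and Hodges-Lehmann pairing is coherent, and a rank ANCOVA p-value beside an unadjusted interval is less so.

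Most of this stands. A reader might infer that the trial is underpowered, or that its sensitivity analysis would restore power the primary has lost; step 1 of the working rules that out. A reader might also infer that ignoring the strata inflates false positives; the direction is the opposite. Nor can a gain be stated as fact, because the pages shown give no correlation of age or baseline with the outcome, and the range starts at nil.

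What the reply does not remove is the mismatch itself. The randomisation factor is used in the key secondary but not in the primary, and no reason is given. Having baseline as the denominator does not in general make percentage change independent of baseline.

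**Conclusion.** The point holds as one of alignment and conditional efficiency, not of validity or lost planned power. On the protocol's own assumptions the primary test reaches its 90%. The forgone gain at the 5% level is nil if neither variable is prognostic and about 1 to 5 points if they explain 5% to 25% of outcome variance. At the 2.5% step the formula gives 85.0% with no adjustment gain and 88.8% at R² = 0.10. If age is prognostic the test is conservative, about 3.8% against a nominal 5% at an assumed correlation of 0.3.

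Confidence is limited by the source. The wording comes from the Amendment 2 change table. The Amendment 3 rows shown make no change to Section 13, but the current protocol body is in Part 1, which is not shown, so a later revision cannot be excluded.

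**What to change.** First confirm that the current protocol body still carries the Section 13.6.2 wording. If it does, then before unblinding:

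- Make the rank ANCOVA already written in 13.6.2.1 (baseline rank, four-level age group, treatment) the primary test for each dose against placebo, with the Hochberg rule unchanged.
- At a minimum, use a van Elteren test stratified by age group. This aligns the test with the randomisation but gains little: about 0 to 2 points in a separate simulation with log-normal frequencies and an assumed age effect.
- Move the plain Wilcoxon to the sensitivity list.
- Keep the Hodges-Lehmann median difference and interval as a descriptive estimate, labelled unadjusted.

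The cost is wording in Section 13.6.2 and the SAP; no new data, patients or programming concept is needed. The small downside is that the unadjusted interval may occasionally disagree with the adjusted p-value, which the text should acknowledge in advance.
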